**Virtual reality-based rehabilitation in the treatment of sarcopenia
among residents in rural caring facilities**

[study protocol]

[name]^a, [name]^b, [name]^b, [name]^a

^a Department of Rehabilitation Medicine, Cishan Hospital, Ministry of Health and Welfare, Kaohsiung, Taiwan; [name]

^b Department of Biomedical Engineering, National Cheng Kung University, Tainan, Taiwan; [name]

Project administrator: [name]., Department of Rehabilitation Medicine, Cishan Hospital, Ministry of Health and Welfare, [name]

[contact], [name]; [contact]
e-mail : [contact]

NCT number: NCT03809104

Date of the document: December, 08, 2019

[Study protocol]

Subject Characteristics and Ethical Statements

It was a prospective non-randomized controlled study, conducting at southern rural Taiwan from January 2019 to October 2019. Older adults aged more than 60 and lived in the nursing home or went to daycare center regularly were recruited for screening. All the residents with sufficient cognitive function and physical fitness to perform training that lasts for 30 minutes and meeting the criteria of sarcopenia by AWGS as the following (1) muscle mass less than 7.0 kg/m^2 for men and 5.7 kg/m^2 for women by using bio-impedance analysis and (2) handgrip strength less than 26 kg for men and 18 kg for women or usual gait speed less than 0.8 m/s), participated the final VR-REH. Participants with the presence of significant cardiopulmonary disease with oxygen supplement, uncontrollable high blood pressure, recent infection, or other diseases prohibited to participate in sports exercise by the American College of Sports Medicine (ACSM) guideline are excluded(1). To determine the sample size, the G*Power software (version 3.1.9.2, for Windows was used. The alpha level and the power were set as 0.05 and 0.8. The effect size was set at high effect (0.8) and the minimal estimated sample size was 15 subjects.

VR-based rehabilitation programs

The program was combined with progressive resistant training and functional movement of dominant upper limb. The device of the VR included one computer, one Oculus Rift headset, one constellation, and one Leap Motion sensor (Figure 1). The Oculus Rift headset uses an organic light-emitting diode (LED) panel for each eye, each having a resolution of 1080×1200 . These panels have a refresh rate of 90 Hz and globally refresh. Oculus Rift headset is portable, lightweight, and works with standard PC hardware. Constellation is the positional tracking system of Oculus Rift, used to track the position of the user's head as well as other VR devices, consisting of external infrared tracking sensors that optically track specially designed VR devices(2). The hand-hold sensor we used was Leap Motion rather than Oculus Touch controller since the hand dexterity of our participants was insufficient generally. The Leap Motion controller is a small universal serial bus peripheral device and could be mounted onto a VR headset. Leap motion is designed for hand tracking in VR by using two monochromatic infrared cameras and three infrared LEDs. It could observe a roughly hemispherical area, to a distance of about 1 meter(3).

The software used in the VR-REH contained 4 different commercialized VR games, including (1) Leap Motion Blocks ®(2) Slum Ball VR Tournament ®(3) VR Super Sports ®10th edition- Basketball (4) VR Super Sports ®10th edition- Soccer (Figure 2), listed in performing order. We analyzed the tasks according to the basis of the motor learning theory of Gentile and selected the game based on body stability and stationary conditions for initial practice(4) (Table 1). Each game was performed by the participants for 6 minutes with the assistance by a well-trained physiotherapist assistant (PTA). There was a one to two minutes break between each game for switching the setting and adjustment for the Oculus Rift headset. One designed mass would be held on the dominant hand of the participants and

the weight increased gradually during the duration of the VR-REH, adjusted by each participant's ability. There was also one 5-minute warm-up and cool-down exercise before and after the VR-REH, respectively. Based on the recommendation of ACSM(1) and previous studies(5), the VR-REH lasted for 12 weeks, twice per week, and 40 minutes per time. There was at least 1-day break between each training.

Baseline screening and outcome measurements

Every participant went through four evaluations in this study. The first evaluation was the baseline evaluation, which was done to make sure the subjects meet the definition sarcopenia before the VR-REH. The second, third, and fourth evaluation was conducted at 4, 8, and 12 weeks after VR-REH, respectively. The primary outcomes included appendicular skeletal muscle mass (ASMM) index (ASMMI), dominant hand grip strength (HGS), and usual gait speed while the secondary outcomes were the range of motion (ROM) of joints of the dominant upper limbs, the strength of the biceps and tricepsbrachii muscles, and the scores of box and block test (BBT).

Anthropometry and Body Composition

Vector bioelectric impedance analysis (VBIA) was used in this study to measure the body composition of participants. VBIA was performed with the bioelectrical impedance vector analysis software by using the resistance–reactance graph method(6). Zeus 9.9 PLUS (Jawon Medical Co. Ltd., KungsangBukdo, South Korea) was used to analyze the body composition. The machine sent a minute electric current and measured the body composition by using personal data that have been saved (height, weight, sex, age, and newly calculated body impedance) via the tetrapolar electrode method (electrodes were located on both hands, both soles of the feet, and both ankles of participants with frequencies of 1, 5, 50, 250, 550, and 1,000 kHz and a current of 360 uA). ASMMI was defined as appendicular skeletal muscle mass (kg) divided by height squared (m^2)(7).

Measurement of dominant hand grip strength

The measurements of the HGS were determined by means of the JAMAR-Dynamometer (J A Preston Corporation, New York, USA) using all five notches. It is a hydraulic instrument measuring the isometric strength in kilograms and numerous studies have investigated the reliability of it in different older populations(8). Each participant was shown the correct handling and positioning of the instruments: they were asked to sit straight, with the upper arm in a neutral position and a 90° flexion of the elbow. The forearm was held in neutral position and the wrist at a 0 to 30° extension. The instrument was held freely: neither the hand nor the forearm was allowed to rest on a surface(9). Three measurements were done and recorded as the average of the three measurements and the participants rested for 1 minute in between measurements.

Measurement of the gait speed

We evaluated the usual gait speed by measuring the time it took for a participant to walk on a 6 meter-long corridor without barrier as suggested by AWGS(7). Timing started after the subject walking and stopped at the point when a subject reached a distance of 6 meters. The gait speed was measured twice and the final measurement was the average of the two. The participant was allowed to rest for 10 minutes in between measurements.

Measurement of range of motion of joints of dominant upper extremity

ROMs of dominant upper extremity that are easily limited in older adults were measured by goniometer under standard positions(10), including shoulder flexion, abduction, and external rotation; elbow flexion and extension; forearm supination and pronation; and wrist flexion and extension.

Measurement of dominant biceps and triceps brachii muscle strength

We used MicroFET®3(Hoggan Health Industries, West Jordan, UT) to measure the maximal voluntary isometric contraction (MVIC) of the biceps and tricepsbrachii muscles. MicroFET®3 is an electronic hand-held dynamometer that could detect 0-150 lbs force with high reliability and validity(11). To measure the MVIC of biceps brachii muscle, the participant was asked to lie on the treatment table with elbow forming a 90-degree angle to the horizontal such that the arm is perpendicular to the limb and the tester placed MicroFET®3 on the ventral side of the arm and align it with the ulnar styloid of the participant. Then, the tester exerted a resistant force towards the device and encouraged the participant to against the force with their maximum strength. To measure the MVIC of triceps brachii muscle, the procedure was the same as in measurement of biceps brachii muscle except that the tester placed the device on the dorsal side of the participant's arm(12). The MVIC was measured twice and the final measurement was the average of the two. The participant was allowed to rest for 1 minute in between measurements.

The box and block test

The set-up of the BBT includes a wooden box with 150 wooden blocks inside. The wooden box is divided into two compartments. One filled with blocks, and the other is empty. During this test, the patient is seated upright in a chair and needs to transfer the wooden blocks, one by one, from one compartment to the other. The patient is scored based on the number of blocks he or she can transfer from one compartment to the other in 60 seconds. The BBT has high test-retest reliability and validity and could measure the unilateral gross manual dexterity in different populations(13).

Table 1. Virtual-reality games corresponding to Gentile's skill categories (27)

		Action function			
		Body stability ^c		Body transport ^c	
Environment context ^a		No object manipulation ^d	Object manipulation ^d	No object manipulation ^d	Object manipulation ^d
Stationary regulatory conditions	No intertrial variability ^b	Leap motion block		Basketball	
	Intertrial variability ^b				
In-motion regulatory conditions	No intertrial variability ^b	Slum Ball VR Tournament		Soccer	
	Intertrial variability ^b				

^aThe regulatory conditions indicate relevant environmental features that constrain movement execution and may either be stationary (stationary regulatory conditions) or moving (in-motion regulatory conditions).

^bWith the indicator, intertrial variability is used to differentiate between regulatory conditions that change between trials (intertrial variability) and those that do not (no intertrial variability).

^cBody orientation indicates whether an action requires the performer to move from one location to another (body transport) or not (body stability).

^dObject manipulation indicates whether an object has to be controlled during the action performance (object manipulation) or not (no object manipulation).

According to Gentile, the easiest skill category can be found at the top left position. Moving either rightward or downward in the table renders the skill category more difficult.

Figure 1.

The hardware of the virtual-reality based rehabilitation. The participant sat or stood 1 meter in front of the screen and was supervised by one well-trained caregiver.

A: Oculus Rift Headset

B: Oculus constellation: sensor for headset

C: Leap Motion: sensor for hand movement

D: Hand-hold device

Figure 2.

The software of the virtual-reality based rehabilitation.

A: Leap Motion Blocks ®

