**Virtual reality-based rehabilitation in the treatment of sarcopenia among
residents in rural caring facilities
[Statistical Analysis Plan]**

[name]^a, [name]^b, [name]^b, [name]^a

^a Department of Rehabilitation Medicine, Cishan Hospital, Ministry of Health and Welfare, Kaohsiung, Taiwan; [name]

^b Department of Biomedical Engineering, National Cheng Kung University, Tainan, Taiwan; [name]

Project administrator: [name]., Department of Rehabilitation Medicine, Cishan Hospital, Ministry of Health and Welfare, [name]

[contact], [name]; [contact]

e-mail : [contact]

NCT number: NCT03809104

Date of the document: December, 08, 2019

[Statistical Analysis Plan]

Sample size estimation

To determine the sample size, the G*Power software (version 3.1.9.2, for Windows) was used. The alpha level and the power were set as 0.05 and 0.8. The effect size was set at high effect (0.8) and the minimal estimated sample size was 15 subjects.

Statistical Analysis

We used SPSS for Windows version 19.0 (Released 2010. Armonk, NY: IBM Corp) for all analyses. Continuous data were expressed as mean \pm SD and categorical variables were presented as absolute numbers or percentages. Normality and homoscedasticity were checked prior to each analysis. For comparisons data between participants in nursing home and daycare center, the chi-square test, independent t-test, and Mann-Whitney U test were used to test for differences in the distribution between categorized, normally distributed, and non-normally distributed variables, respectively. A change in outcome measures among baseline, 1, 2, and 3-month postVR-REH were assessed using repeated measure one-way analysis of variance (ANOVA) and a Bonferroni post-hoc test. A P value $\leq .05$ was considered statistically significant.

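### The study is labelled controlled, but no control condition is described and change is tested over time only

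*Protocol*

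**What the plan says.** The protocol, under Subject Characteristics and Ethical Statements, gives the design label: "It was a prospective non-randomized controlled study". The same paragraph describes who was treated, beginning "All the residents with sufficient cognitive function and physical fitness to perform training" and ending with their participation in VR-REH, provided they met the sarcopenia criteria. It names nursing homes and daycare centers as the places of recruitment.

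The protocol's section on the VR program describes one intervention. Under Baseline screening and outcome measurements there is one schedule for all: "Every participant went through four evaluations in this study". The same section says: "The first evaluation was the baseline evaluation, which was done to make sure the subjects meet the definition sarcopenia before the VR-REH". It also names the endpoints: "The primary outcomes included appendicular skeletal muscle mass (ASMM) index (ASMMI), dominant hand grip strength (HGS), and usual gait speed".

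The SAP, under Statistical Analysis, plans two things. The first is a set of tests introduced by "For comparisons data between participants in nursing home and daycare center". The second is the test of change: "A change in outcome measures among baseline, 1, 2, and 3-month postVR-REH were assessed using repeated measure one-way analysis of variance (ANOVA"), followed by Bonferroni post-hoc comparisons. On sample size, both documents give alpha 0.05 and power 0.8, and state: "The effect size was set at high effect (0.8) and the minimal estimated sample size was 15 subjects".

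**The concern.** A controlled study, randomized or not, has a comparator. Here no group receives anything other than VR-REH, no rule assigns anyone to a comparator, and no planned analysis contrasts treated with untreated participants. The label leads a reader to expect a contrast that the plan does not contain.

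What is at stake is how the results are read. A time-only test attributes all change from baseline to time on the program. Two sources of change unrelated to VR-REH follow directly from the text:

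- **Regression to the mean.** Participants are selected for low muscle mass plus low grip strength or low gait speed. These three measures are the primary outcomes, and the evaluation that confirms eligibility is also the baseline.
- **Repeat testing.** Everyone takes the same performance tests four times, so familiarity with the tests can raise scores.

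**Working it through.** **1. Is there a comparator anywhere in the documents?**

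| Element | Where | What is there |
|---|---|---|
| Design label | Protocol, Subject Characteristics | Controlled, not randomized |
| Who is treated | Same paragraph | All eligible residents |
| Conditions described | Protocol, VR program section | VR-REH only |
| Assessments | Protocol, Baseline screening | One schedule for everyone |
| Allocation rule | Neither document | None |
| Between-group test | SAP, Statistical Analysis | Nursing home vs daycare center |
| Test of change | SAP, Statistical Analysis | One-way ANOVA: time is the only factor |

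The setting comparison does not supply a control. Nothing assigns either setting to a control condition. As the text reads, both settings receive VR-REH, although no sentence says so expressly. The SAP does not say which variables are compared, and the test of change ignores setting.

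**2. Which design does the stated sample size fit?**

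Inputs from both documents: alpha 0.05, power 0.80, effect size 0.8, n = 15. The test family, the effect-size metric and the sidedness are not stated. Two-sided testing is assumed first.

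*One group, paired t-test.* The statistic is noncentral t with n − 1 df and noncentrality dz·√n.

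- n = 14: 0.8·√14 = 2.993, power 0.790
- n = 15: 0.8·√15 = 3.098, power 0.821

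So 15 is the smallest n that reaches 0.80, and the stated figure is reproduced. One-sided, the minimum would be 12.

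*Two independent groups, d = 0.8.* Noncentrality is d·√(n/2) with 2n − 2 df, where n is the number per group.

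- Two-sided, 25 per group: 0.8·√12.5 = 2.828, power 0.791
- Two-sided, 26 per group: 0.8·√13 = 2.884, power 0.807, so 52 in total
- One-sided, 20 per group: power 0.799; 21 per group: power 0.817, so 42 in total

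Fifteen participants split 7/8 would have two-sided power of about 0.30. Fifteen per group would have about 0.56.

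*Other readings.* For a one-group repeated-measures ANOVA with four times, f = 0.8 gives n = 3 to 6 for assumed within-subject correlations of 0.8 to 0. A two-group ANOVA with f = 0.8 does give a total of 15 (16 with equal groups), but for two groups d = 2f = 1.6.

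**3. How large could regression to the mean be? (Illustration only.)**

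The documents give no SD, test-retest correlation or screening yield. Suppose a normal measure is selected below a cut-off that a proportion p of those screened fall under, with test-retest correlation r. The expected rise at retest, in screening-population SD, is

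(1 − r) · φ(z_p) / p

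| p (assumed) | r (assumed) | Calculation | Rise (SD) |
|---|---|---|---|
| 0.3 | 0.80 | 0.20 × 0.3477 / 0.3 | 0.232 |
| 0.5 | 0.90 | 0.10 × 0.3989 / 0.5 | 0.080 |
| 0.7 | 0.95 | 0.05 × 0.3477 / 0.7 | 0.025 |

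This treats muscle mass as one truncated normal variable. The actual rule has sex-specific cut-offs and a second criterion (grip or gait). No figure is offered for grip strength, gait speed or the repeat-testing effect.

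**The case against.** No text in either document supplies a control group, so the best case on the other side concerns weight and support.

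- **It is only a label.** The SAP speaks of change in outcomes and states no treatment-effect estimand, and a before-after design is legitimate in a small study. Both points are true. The criticism is not of choosing that design. It is that the stated design differs from the one described and analyzed, and readers rely on the stated one.
- **A non-randomized control would not necessarily remove regression to the mean.** This also stands: such a comparator may be poorly matched. It would still give some concurrent measure of change without VR-REH, and here there is none.
- **The sample size proves little.** Agreed in part. The G*Power test is not named, the ANOVA actually planned does not reproduce 15 at f = 0.8, and a two-group reading at f = 0.8 does. That last reading requires d = 1.6, twice the 0.8 in the documents if that figure is read as d. The match is supporting evidence only, and the finding does not need it.
- **The regression figure is assumed.** It is, and its lower end is negligible. Averaging three grip readings and two gait readings, as the protocol specifies, also reduces within-session error for those outcomes. The direction of the bias is sound; its size is unknown.

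**Conclusion.** The concern holds and should be corrected before any result is reported. The protocol calls the study controlled, but the recruitment, intervention, assessment and analysis text describes a single treated group followed over time. That conclusion comes from the text alone and needs no assumption beyond reading both settings as receiving VR-REH.

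The sample size agrees with it: 15 is the one-group minimum at dz = 0.8, against 52 for two groups at d = 0.8 (42 if one-sided), on the assumption that 0.8 is a standardized mean difference. The possible size of the bias cannot be derived from the documents. The 0.02 to 0.23 SD range for muscle-mass index only shows what the stated assumptions imply. The planned ANOVA can estimate mean change in people who received VR-REH; it cannot estimate the effect of VR-REH.

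**What to change.** **If there was no control group**, replace the design label in the protocol with *single-arm before-after study*. Keep the SAP's reference to change and add:

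> The ANOVA estimates mean change from baseline in participants who received VR-REH. There is no concurrent control, so this change will not be reported as a treatment effect. The nursing home versus daycare comparison is descriptive and is not a control comparison.

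Also name the test behind the sample size of 15. The cost is wording in two documents and a more modest conclusion, with no new data or patients.

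**If a control group did exist**, describe it and how participants were assigned to it, specify a group-by-time comparison as the main analysis, and restate the sample size for two groups. The study ran from January to October 2019 and both documents are dated December 2019. Such an analysis should therefore be labelled post hoc unless earlier specification can be shown, and the revised power statement should be identified as retrospective. The cost is the description, the added analysis and the revised power statement.

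### Do follow-up visits timed 4, 8 and 12 weeks after a 12-week programme leave the trial with no end-of-training evaluation?

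*Protocol*

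**What the plan says.** Protocol, VR-based rehabilitation programs: "the VR-REH lasted for 12 weeks, twice per week, and 40 minutes per time".

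Protocol, Baseline screening and outcome measurements: "Every participant went through four evaluations in this study". The first is a screening and baseline visit, "which was done to make sure the subjects meet the definition sarcopenia before the VR-REH". For the other three: "The second, third, and fourth evaluation was conducted at 4, 8, and 12 weeks after VR-REH, respectively".

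SAP, Statistical Analysis, on the same four occasions: "A change in outcome measures among baseline, 1, 2, and 3-month postVR-REH were assessed using repeated measure one-way analysis of variance (ANOVA"), with Bonferroni post-hoc comparisons.

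The protocol and SAP agree in direction: one says after, the other says post. Neither says whether the count starts at the first or the last training session. Neither describes a separate end-of-training visit, a follow-up phase once training has stopped, or an aim of studying whether gains persist.

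**The concern.** A course that lasts 12 weeks, followed by evaluations 4, 8 and 12 weeks after it, puts every follow-up value in a period when participants are no longer training. With only four evaluations in total, and the first taken before training, no visit is left for the end of the course. The SAP repeats the same direction, so the wording is not an isolated slip in one sentence.

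If that schedule were the real one, the effect at the end of training could not be estimated, and any loss of gain after stopping would be mixed into all the follow-up data on the three primary outcomes (muscle mass index, grip strength, gait speed). If the visits were in fact made during the course, describing them as post-programme could lead a reader to think the gains had been shown to last. The two readings answer different clinical questions, so it is reasonable to ask which one holds.

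**Working it through.** **Inputs.** Course length 12 weeks at 2 sessions per week (Protocol, VR-based rehabilitation programs). Follow-up offsets 4, 8 and 12 weeks, four evaluations in all (Protocol, Baseline screening and outcome measurements). Offsets 1, 2 and 3 months (SAP, Statistical Analysis). Study window January to October 2019 (Protocol, Subject Characteristics and Ethical Statements).

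**1. The two timelines, in weeks from the first session.** Planned sessions are 12 × 2 = 24.

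| Evaluation | Counted from first session | Sessions by then | Counted from last session | Sessions by then |
|---|---|---|---|---|
| 2nd | 4 | 4 × 2 = 8 | 12 + 4 = 16 | 24 |
| 3rd | 8 | 8 × 2 = 16 | 12 + 8 = 20 | 24 |
| 4th | 12 | 12 × 2 = 24 | 12 + 12 = 24 | 24 |

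The readings differ by 12 weeks at every visit. On the first, the fourth evaluation coincides with the end of training. On the second, no evaluation does.

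**2. Does the calendar decide?** The study is described as "conducting at southern rural Taiwan from January 2019 to October 2019". From 1 January to 31 October is 303 days, or 303/7 = 43.3 weeks. From 31 January to 1 October is 243 days, or 34.7 weeks. A 12-week and a 24-week participant timeline both fit, so it does not.

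**3. Do weeks and months conflict?** At 30.4375 days per month, 1, 2 and 3 months are 4.3, 8.7 and 13.0 weeks, against 4, 8 and 12. The largest gap is about 1 week. This is rounding and does not help choose between the readings.

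**4. How is the programme's name used?** In one place it is the 12-week course. In another it is part of a single session: "There was also one 5-minute warm-up and cool-down exercise before and after the VR-REH, respectively". The session arithmetic agrees. Four games of 6 minutes with three breaks of 1 to 2 minutes give 24 + 3 = 27 to 24 + 6 = 30 minutes. Taking 5 minutes each for warm-up and cool-down brings this to 37 to 40 minutes, which matches the stated 40. So after VR-REH does not have one fixed meaning in the protocol.

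**5. What would the later schedule measure?** Baseline precedes training and is one of the four levels in the ANOVA. Every contrast with it is therefore a change from the pre-training value, that is, response net of any loss since training stopped. Retention proper needs an end-of-training value as its reference, which that schedule lacks. So even on that reading it would be wrong to say that the trial measures retention instead of response.

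**6. Does the analysis depend on the reading?** The one-way repeated-measures ANOVA treats time as a factor with four levels. It uses which values belong to which evaluation, not the number of weeks between them. The F test and the 4 × 3/2 = 6 pairwise comparisons are the same under either timeline.

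**7. The sample size.** The stated 15 is reproduced by a two-sided paired t-test with standardised effect 0.8 and alpha 0.05: power is 0.821 at n = 15 and 0.790 at n = 14. The plan ties this figure to no visit, so it does not settle the timing. As an illustration only, suppose the 0.8 applied at the end of training and 25% or 50% of it were lost by the visit. The effect would be 0.6 or 0.4, and power at n = 15 would be 58% or 30%. The documents give no such loss.

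**The case for a change.** The strongest case for acting is that the text needs attention whichever reading is true. In the protocol's own paragraph on evaluations, baseline is before the programme and follow-up is after it, so the programme there most naturally means the whole course, and the SAP says the same. If the visits were made during training, both documents mislabel them, and two of the three values come from people who had completed about 8 and 16 of 24 planned sessions. If they were not, there is no end-of-training value. A reader of a significant result could not tell which effect was seen, and one sentence would settle it at no cost.

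Much of this stands: the time origin is undefined and the wording is loose. What does not stand is the step from an undefined origin to a design flaw. The protocol and SAP do not contradict each other, and the course length contradicts neither of them. The harm from a claim of lasting benefit is hypothetical, since neither document makes or plans one. It is also true that the SAP names no primary time point, but that would be so under either timeline and is a separate matter.

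**Conclusion.** No change to the plan follows. This is a missing detail of wording that analysts can fill from records. The open quantity is the origin of the time count, worth 12 weeks at each visit (weeks 4, 8 and 12, or weeks 16, 20 and 24). The documents do not settle it, though the match between the visit times and the 12-week course, together with the absence of any described post-training phase, makes visits during and at the end of training at least as plausible as the later schedule.

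Writing the origin down would record what was done. It would move no visit and would change neither the ANOVA, its 6 pairwise comparisons nor the sample size of 15. Both documents are dated December 2019, after the October 2019 end of the study, and the protocol reports the evaluations in the past tense, so anyone reporting the results can describe each value by its actual date.

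This conclusion assumes that visit dates were recorded, and that the results are described in line with them: as change during and at the end of training, or as change from baseline some weeks after it. If the later schedule proved to be the real one, the lack of an end-of-training value would be a limitation to report, and no rewording of the plan could supply it.

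### Three unranked primary outcomes are each tested at P ≤ .05 with no success rule or adjustment across them; if any one counts as success, the false-positive risk is about 9% to 14% (assumed correlations .9 to 0, sphericity).

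*Protocol*

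**What the plan says.** The Protocol, under Baseline screening and outcome measurements, says: "The primary outcomes included appendicular skeletal muscle mass (ASMM) index (ASMMI), dominant hand grip strength (HGS), and usual gait speed". It gives no order among the three. Under Subject Characteristics and Ethical Statements the same three measures enter the sarcopenia entry criterion: low muscle mass together with "handgrip strength less than 26 kg for men and 18 kg for women or usual gait speed less than 0.8 m/s".

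The SAP, under Statistical Analysis, says that changes from baseline to months 1, 2 and 3 "were assessed using repeated measure one-way analysis of variance (ANOVA) and a Bonferroni post-hoc test", and that a P value of .05 or below "was considered statistically significant". It mentions checks of normality and homoscedasticity, but no check of or correction for sphericity.

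Under Sample size estimation the SAP says: "The alpha level and the power were set as 0.05 and 0.8". It adds: "The effect size was set at high effect (0.8) and the minimal estimated sample size was 15 subjects". No outcome is named there.

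On timing, the Protocol describes the study as "conducting at southern rural Taiwan from January 2019 to October 2019". The SAP carries "Date of the document: December, 08, 2019", and the Protocol bears the same date.

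**The concern.** A one-way repeated-measures ANOVA handles one outcome at a time, so the plan yields three primary omnibus tests, each judged at .05. The Bonferroni test is attached to that ANOVA and adjusts comparisons between visits. It does nothing across muscle mass, grip strength and gait speed.

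The documents leave open whether one significant primary is enough, whether all three are needed, or whether these are three separate questions. Because the three measures together define the condition being treated, reading them as one family is realistic. A reader of a positive primary result therefore cannot tell which error rate applies, and one outcome out of three could be presented as success by chance.

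**Working it through.** **Inputs from the documents.** Three primary outcomes; four evaluations (baseline and weeks 4, 8 and 12); per-test threshold .05; n = 15; effect size 0.8, metric not named.

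**Assumed inputs, because the documents give none.** Correlation between the outcomes' within-person changes (0 to .9), correlation between visits, and the shape of change over time.

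**1. The plan's own figure.** A two-sided paired t-test with standardised change 0.8 and alpha .05 has power .790 at n = 14 and .821 at n = 15. This reproduces 15 subjects. It is one test at the full .05, with no allowance for three primaries, and it is not the planned ANOVA.

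**2. Independent outcomes.** P(at least one false positive) = 1 − (1 − .05)³ = 1 − .8574 = .1426, or 14.3%.

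**3. Correlated outcomes.** The planned ANOVA was simulated with all three outcomes null, n = 15, four visits, F on 3 and 42 degrees of freedom, sphericity, and 200,000 trials per correlation:

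| Correlation between outcomes | Any one ≤ .05 | All three ≤ .05 | Any rejection with Holm |
|---|---|---|---|
| 0 | 14.3% | 0.01% | 4.9% |
| .3 | 13.8% | 0.05% | 4.8% |
| .5 | 12.9% | 0.2% | 4.7% |
| .7 | 11.4% | 0.7% | 4.1% |
| .9 | 8.8% | 2.1% | 3.2% |

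**4. Sphericity relaxed.** The setup is the same, but visits follow an assumed AR(1) correlation and the F-test is uncorrected (40,000 trials).

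- AR(1) .5: the any-one risk is 10% to 16%. Holm gives 6.6%, 6.0% and 4.3% at between-outcome correlations 0, .5 and .9.
- AR(1) .8: the any-one risk is 11% to 19%. Holm gives 8.9%, 7.9% and 5.5%.

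Holm on uncorrected P values therefore does not guarantee .05. With a Greenhouse-Geisser correction, Holm stayed below 5% in every case run.

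**5. Power cost of Holm's first step (.05/3 = .0167).** This uses the noncentral F with residual SD 1, sphericity, and a baseline-to-week-12 change of .8 × √2 = 1.131. The noncentrality λ is 15 times the sum of squared deviations of the four visit means from their average.

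- Linear change: deviations are ±.566 and ±.189, so λ = 15 × 2 × (.320 + .0356) = 10.67. Power falls from 74.8% to 57.8%.
- One step at week 4 or week 12: λ = 15 × 1.28 × ¾ = 14.4. Power falls from 87.4% to 74.9%.
- Weeks 4 and 8 both halfway (the least favourable shape): λ = 15 × 2 × .32 = 9.6. Power falls from 69.8% to 52.0%.

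If all three effects are present, Holm's later steps recover part of this. Average power per outcome under linear change is then 64% to 67%.

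**The case against.** **Three distinct constructs may be reported as three separate claims, and adjustment is then not required.** This stands. Each test then has its own nominal 5% rate. It limits the remedy to claims of overall benefit that rest on one or more of the three. The documents do not adopt this reading, so it does not close the gap.

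**The any-one rule is nowhere stated.** This also stands. A reader might infer that the trial's primary error rate simply is 14%, or that the team intended to claim success on whichever outcome came out significant. The documents support neither inference. The 9% to 14% is conditional on that rule, and if all three must be significant there is no inflation.

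**It is too late to fix.** This stands in part. Both documents are dated after the stated study end, so nothing added now is prespecified. Choosing an all-three rule, a single primary or a fixed order at this stage would not control the error rate. A labelled adjustment shown beside the unadjusted P values still tells the reader how strong the evidence is. The dates alone do not show that results had been seen when the plan was written, and this point does not claim it.

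**The null may itself be optimistic.** Participants are selected on the same measures at the baseline evaluation. If that evaluation is also the ANOVA baseline, regression to the mean produces apparent improvement without true change. As an illustration, with assumed reliability .90, selection below the 30th percentile and n = 15, a single outcome would be significant 14.6% of the time at .05 and 6.5% at .0167. Adjustment across outcomes does not remove this.

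**Conclusion.** The concern holds conditionally. Three unranked primaries are tested at .05 each, with no rule or adjustment across them.

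- If any one counts as success, the chance of at least one false positive is about 9% to 14% under sphericity (assumed between-outcome correlations .9 to 0).
- It is about 10% to 19% with assumed serial correlation between visits (AR(1) .5 to .8) and an uncorrected F-test.
- If all three are required, there is no inflation (about 2% or less when all are null).
- If they are three separate claims, each carries its own nominal 5%.

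The omission is certain from the text. The size rests on the assumed correlations and on an any-one rule that the documents do not state. The figures cover the three omnibus tests only, not the secondary outcomes or the comparison of nursing home with daycare participants.

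A reader might infer that adjusting across outcomes would make a positive result evidence that the VR programme works. It would not. It addresses chance findings in before-after change and says nothing about what caused the change.

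**What to change.** Keep the planned ANOVAs and Bonferroni post-hoc tests, leave the secondary analyses unchanged, and add one SAP paragraph along these lines:

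> Omnibus P values for ASMMI, HGS and gait speed use the Greenhouse-Geisser correction. Any overall claim of benefit resting on one or more of these three outcomes uses the Holm procedure across the three P values (smallest against .0167, next .025, last .05). Unadjusted P values for all three are shown beside it. No success rule was prespecified; this adjustment was added after the end of the study. The overall .05 covers the omnibus tests, not pairwise comparisons between visits. It does not remove regression to the mean from selection on the same measures at baseline, if that evaluation is the ANOVA baseline, and does not show that the programme caused any change.

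Do not replace this with an all-three rule, a single primary or a fixed order chosen now. If the outcomes are reported only as three separate claims, show all three, each at its nominal 5%, and say that no rule was prespecified.

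The cost is one paragraph and one reporting note, with no new data. Single-outcome power falls at Holm's first step by the amounts worked out above, for example from 75% to 58% for linear change, and somewhat further with the sphericity correction. Pairwise claims remain outside the .05. If all three outcomes change only at week 12 (assumed standardised change .8, sphericity), the chance of any false pairwise claim after Holm is about 4% to 7%.
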